## 8.6 Interim Analyses and Data Monitoring

Interim analysis is not defined in protocol and will not be performed in this study.

## 8.7 Adjustments for Multiplicity

The baseline characteristics will be compared between the matched patients to check the balance of baseline characteristics between the two sub-groups of Cohort B after propensity score matching (PSM). There will be no multiple comparisons in this study. As a result, adjustment for multiplicity is not applicable in the analysis.

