### 6.2 Endpoints

#### 6.2.1 Primary Endpoint(s)

##### Cohort A (patients switched from VKA to Pradaxa®)

- Mean PACT-Q2 scores at the second (30-45 days) and the last assessment (150-210 days) compared to baseline assessment.

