##### Cohort B (patients newly initiated Pradaxa® or VKA)

- Mean PACT-Q2 scores at the second (30-45 days) and the last assessment (150-210 days) compared between 2 treatment groups.

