##### Cohort B (patients newly initiated Pradaxa® or VKA)

- Mean difference in the PACT-Q2 scores at the second (30-45 days) and the last assessment (150-210 days) compared between 2 treatment groups. The difference will be calculated as (PACT-Q2 scores of *Pradaxa®* minus PACT-Q2 scores of VKA at Visit 2, PACT-Q2 scores of *Pradaxa®* minus PACT-Q2 scores of VKA at Last Visit).

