### 11.3 Primary Endpoint Analysis

Mean values and mean change from baseline of PACT-Q2 scores will be presented as descriptive statistics including Number, Mean $\pm$ SD, Median, Range, inter-quartile range (IQR), 25th percentile, 75th percentile and 95% C.I. The changes under Cohort A will be calculated as (PACT-Q2 scores at Visit 2 minus PACT-Q2 scores at visit 1, PACT-Q2 scores at Last Visit minus PACT-Q2 scores at visit 1). The difference under cohort B will be calculated as (PACT-Q2 scores of Pradaxa® minus PACT-Q2 scores of VKA at Visit 2, PACT-Q2 scores of Pradaxa® minus PACT-Q2 scores of VKA at Last Visit). Shapiro-Wilk test will be conducted for testing the normality. If the null hypothesis of normally distributed of Shapiro-Wilk test is not reject, two-sided paired t-test will be performed and obtain the p-value. Significant level of the test will be set as 0.05. Once significant result of Shapiro-Wilk test is lower than 0.05, Wilcoxon signed rank test will be used instead.

For cohort B, the patients newly initiated Pradaxa® or VKA will be matched with a ratio of 1:1 based on the propensity score with caliper matching. After the propensity score each patient is generated, both Pradaxa® group and VKA group should be randomly sorted and then the first VKA unit is selected to find its closest

Pradaxa® match in terms of the propensity score. The random seed will be set as 20190218. The caliper will be set as 0.001.

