## 11.4 Secondary Endpoint Analyses

### Cohort A (patients switched from VKA to Pradaxa®)

- Mean change in the PACT-Q2 score at the last assessment (150-210 days) compared to the second assessment (30-45 days). The change will be calculated as (PACT-Q2 scores at Last Visit minus PACT-Q2 scores at visit 2). The test hypothesis of MMSE will be  $H_0: \text{Change} = 0$  vs.  $H_a: \text{Change} \neq 0$ . Shapiro-Wilk test will be conducted for testing the normality. If the null hypothesis of normally distributed of Shapiro-Wilk test is not rejected, two-sided paired t-test will be performed and obtain the p-value. Significant level of the test will be set as 0.05. Once significant result of Shapiro-Wilk test is lower than 0.05, Wilcoxon signed rank test will be used instead.

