## 11.6 Interpretation and Conclusion

The study objective is to provide evidence to show if significant change of PACT-Q2 scores in patients treated with Pradaxa® or VKA. The hypothesis testing for the primary endpoint will be two-sided and significant level will be 0.05. Once the significant is found (p-value < 0.05), the study shows the significant change of PACT-Q2 scores in patients treated with Pradaxa® or VKA.

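### SAP 8.7 waives multiplicity adjustment on a ground that the SAP's own primary endpoints contradict, and SAP 11.6 does not say which comparison carries the conclusion

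*SAP*

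**What the plan says.** SAP 8.7 states "There will be no multiple comparisons in this study" and infers that adjustment does not apply. It gives no other reason.

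The primary endpoints are in SAP 6.2.1 and are restated in 10.2:

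- Cohort A: "Mean PACT-Q2 scores at the second (30-45 days) and the last assessment (150-210 days) compared to baseline assessment".
- Cohort B: "Mean PACT-Q2 scores at the second (30-45 days) and the last assessment (150-210 days) compared between 2 treatment groups".

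SAP 11.3 defines a separate change or difference for each visit and, for the primary test, says "Significant level of the test will be set as 0.05". Protocol 9.7 makes all tests two-sided at 0.05. Protocol 9.7.1 has the two Cohort A follow-up visits each compared with baseline in turn. SAP 11.4 adds a secondary Cohort A test, last visit against Visit 2, also at 0.05.

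SAP 11.1 gives one hypothesis for the whole study: change equal to zero. SAP 11.6 then gives the rule for the conclusion: "Once the significant is found (p-value < 0.05), the study shows the significant change of PACT-Q2 scores". The sentence goes on to refer to patients on either drug.

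**The concern.** A reader of SAP 8.7 is told that multiplicity does not arise, although the report will carry at least four primary p-values and one secondary. SAP 11.6 is the only place that turns p-values into a conclusion. It does not say which cohort or visit counts, or whether one or both visits must be significant. I found no hierarchy or both-visits rule elsewhere in the two documents. One significant result, in one cohort at one visit, could therefore be reported as the finding of the study.

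The wording of that finding is a second problem. SAP 11.6 would have it that "the study shows the significant change of PACT-Q2 scores in patients treated with Pradaxa® or VKA". Cohort B patients first complete PACT-Q2 at Visit 2, so VKA initiators have no baseline score from which a change could be measured. What is planned for them is a between-group difference, which the hypothesis in SAP 11.1 does not describe.

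**Working it through.** Neither document states a familywise error rate or a power figure, so there is no plan figure to reproduce. The only error input is the per-test level of 0.05.

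**1. Count of tests, assuming one PACT-Q2 score per comparison**

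| Cohort | Comparison | Status | Source |
|---|---|---|---|
| A | Visit 2 minus baseline | primary | SAP 10.2, 11.3 |
| A | Last visit minus baseline | primary | SAP 10.2, 11.3 |
| B | Pradaxa minus VKA, Visit 2 | primary | SAP 10.2, 11.3 |
| B | Pradaxa minus VKA, last visit | primary | SAP 10.2, 11.3 |
| A | Last visit minus Visit 2 | secondary | SAP 11.4 |

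Protocol 9.3.5 gives PACT-Q2 three dimensions: convenience, burden, and satisfaction. Neither document defines a total score or names the score to be tested. If each dimension is tested, every count is multiplied by three: six primary tests per cohort.

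**2. Error within one cohort if either visit suffices**

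Treat the two test statistics as standard normal with correlation r and no true effect:

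P(at least one p < 0.05) = 1 − P(|Z1| < 1.96 and |Z2| < 1.96).

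The documents give no value of r, so a range is assumed.

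| r | 0 | 0.3 | 0.5 | 0.7 | 0.9 |
|---|---|---|---|---|---|
| P(at least one) | 9.75% | 9.51% | 9.07% | 8.35% | 7.04% |

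At r = 0 this is 1 − 0.95² = 9.75%.

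**3. Where r may lie in Cohort A**

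Both changes share the same baseline. With equal variances, r = (1 + v − 2b) / (2(1 − b)), where b is the baseline-to-follow-up correlation and v the Visit 2-to-last-visit correlation.

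- If v = b, r = (1 − b) / (2(1 − b)) = 0.5, giving 9.07%.
- If b = 0.3 and v = 0.7, r = 1.1/1.4 = 0.786, giving 7.9%.

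Both fall inside the 7.0% to 9.5% range.

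**4. Error if both visits must be significant**

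The error cannot exceed that of either single test, so it is at most 5%. With no effect at either visit it is 0.10 − P(at least one): 0.10 − 0.0951 = 0.5% at r = 0.3, and 0.10 − 0.0704 = 3.0% at r = 0.9.

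**5. Does the conclusion fit Cohort B?**

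The schedules (Protocol Table 1, SAP Table 7.1) show PACT-Q2 at baseline for Cohort A only. Protocol 9.3.5 says the same. SAP 10.2 and 11.3 define the Cohort B contrast correctly as Pradaxa minus VKA. SAP 11.1 and 11.6 do not follow that definition.

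**The case against.** The strongest objection is that the study is descriptive. The protocol abstract says so, the objective is to describe treatment perception, and there is no power calculation. Unadjusted p-values are defensible in such a study. That stands and lowers the severity. It does not rescue SAP 8.7, which does not rely on the descriptive aim but denies that the comparisons exist. Nor does it remove the significance rule in SAP 11.6.

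It can also be said that SAP 10.2 and 11.3 set out the Cohort B contrast plainly, so an analyst would not compute the wrong quantity. That is fair: the defect lies in what may be concluded, not in what will be calculated.

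Four stronger readings are tempting but not supported:

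- **The 7.0% to 9.5% holds unconditionally.** It needs either visit alone to be enough. SAP 11.6 permits that but does not state it.
- **The study-wide error is about 14% to 18%.** Treating the cohorts as independent and using the same r in both, 1 − (1 − 0.0704)² = 13.6% at r = 0.9 and 1 − (1 − 0.0951)² = 18.1% at r = 0.3. This applies only if any one of four primary tests may carry the conclusion, which the SAP does not say.
- **No test is named.** SAP 11.2 and 11.3 name the paired t-test, or the Wilcoxon signed-rank test if normality is rejected. What is missing is the cohort and visit.
- **The Cohort B difference has no confidence interval.** SAP 11.3 mentions intervals for means and changes from baseline, but SAP 8.12 includes a 95% interval in the summary of continuous variables generally.

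**Conclusion.** SAP 8.7 is wrong as written. There are at least two primary 0.05 tests in each cohort and one secondary test in Cohort A, and more if the PACT-Q2 dimensions are tested separately. SAP 11.6 leaves open which of them supports the conclusion and words it in a way that cannot apply to VKA initiators.

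The false-positive chance within a cohort is about 7.0% to 9.5% against a nominal 5%. That rests on either visit being sufficient, one score per comparison, and assumed correlations of 0.9 to 0.3. With both visits required there is no inflation.

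Severity is minor to moderate. The planned estimates stand, and the correction concerns what the report may conclude from them.

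**What to change.** 1. Correct SAP 8.7 to acknowledge the comparisons, and name the PACT-Q2 score or scores to be tested.
2. Reword SAP 11.1 and 11.6 so that each hypothesis and conclusion names its cohort and visit: change after switching in Cohort A, Pradaxa–VKA difference in Cohort B. Drop the reference to a change in VKA patients.
3. In keeping with the descriptive objective, delete the significance rule in SAP 11.6, state in 8.7 that the p-values are unadjusted and descriptive, and base interpretation on each estimate with the 95% interval that 8.12 already provides for.

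These are wording changes and cost no power.

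If formal conclusions are to be kept, apply Holm at two-sided 0.05 over all primary tests within each cohort and leave the secondary test descriptive. The costs below take 80% power as a reference point, since the plan sets none:

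- **Two tests, first step at 0.025:** the detectable effect rises by (2.241 + 0.842)/(1.960 + 0.842) = 1.10, about 10%. An effect with 80% power at 0.05 has P(Z > 2.241 − 2.802) = 71%.
- **In SD units, (z + 0.842)/√n at planned numbers before losses:** in Cohort A (300 patients), 0.162 becomes 0.178 SD of the change. In Cohort B, with at most about 200 pairs because about 200 VKA patients are planned, 0.198 becomes 0.218 SD of the paired difference.
- **Six tests, if the three dimensions are tested separately, first step at 0.05/6 = 0.0083:** (2.638 + 0.842)/2.802 = 1.24, about 24%, and power falls to P(Z > 2.638 − 2.802) = 56%.

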## 8.8 Multi-center Studies

1000 patients will be enrolled from 20 sites in Taiwan. With the intention of pooling the data for analysis, all the investigators from participating institutions will follow the study protocol and conduct the clinical trial to improve the consistency across centers. All the data defined on CRF will be collected and managed via a centralized process. The collected clinical data will be summarized with respect to demographic characteristics, and efficacy and safety observations.

## 8.9 Data Management System and Analysis Software

The data collected will be entered into the study database against the paper CRF and stored in the Clinical Data Management Systems (CDMS). The data backup is exhibited by data management personnel. The data will be exported to Statistical Analysis System® (SAS) for Windows (Version 9.4 or higher, SAS Institute, Cary, North Carolina, USA) to generate the subject listings, tabulations, and statistical analyses.

## 8.10 Coding Dictionary

In order to create a standard language that is comparable across all therapeutic teams and provide standardization for statistical analysis, adverse events recorded on the paper CRF will be coded by medical dictionaries/thesaurus. In this study, the Medical Dictionary for Regulatory Activities (MedDRA) version 21.1 or higher will be used to map adverse events verbatim to Preferred Terms (PT) and System Organ Class (SOC).

## 8.11 Data Handling and Transfer

All collected clinical data will be collected via paper CRF by study coordinator, and will be managed centralized and stored in the clinical data management systems. No external data will be imported to the system. The system of variable coding will follow rules of SOPs. During the study, Data manager will follow the SOP to enter and manage the CRFs. After data clean and data lock process, all the clinical data will be exported as SAS datasets and stored in a read-only space. Statistician will perform the statistical analysis based on the SAS datasets.

## 8.12 Programming Specifications

The summary statistics for continuous variables will be entitled as Number, Mean±SD, Median, Range, inter-quartile range (IQR), 25th percentile, 75th percentile and 95% C.I. in the table, which represent the number of observations, mean value plus/minus standard deviation, median value of observations, minimum and maximum, lower bound and upper bound of the 95% confidence interval. Range (minimum and maximum) and 95% confidence interval (lower and upper bound) are given in parentheses.

Unless otherwise noted, the summary statistics for continuous variables will be printed out to one decimal place except for the standard deviation and confidence interval. The standard deviation and confidence interval will be expressed to 2 decimal places. If the summary statistics cannot be obtained, it will be printed as “--”

For categorical variables, number and percentage will be presented as summary statistics. All table percentages will be reported with one decimal point unless otherwise specified.

The p-value will be reported to 4 decimal places. An asterisk indicates the statistical significance. P-value less than 0.0001 will be reported as “<0.0001\*” and p-value greater than 0.9999 will be expressed as “>0.9999”. If the p-value cannot be computed, p-value

will be printed as 'NA'.

DRAFT

## 9 SUMMARY OF STUDY DATA

Continuous variables will be summarized by descriptive statistics: number of observations, mean, median, standard deviation, range, and quartiles. Frequency counts and percentages of observed levels will be reported for categorical variables. The denominator of percentages will be the number of subjects with valid assessment results. Subjects with missing data will not be included in the number of denominator.

Efficacy analysis will be performed based on FAS. Safety analysis will be conducted based on Safety population. The relevant population size will be annotated in the tables.

### 9.1 Disposition of Subjects

The number of subjects screened, number of eligible subjects, and number of subject reached study completion will be counted and summarized. The denominator of percentage of number of eligible subjects will be the number of subject screened. The denominator of percentage of number of subject complete the study will be the number of eligible subjects. The summary of reason for early termination will be provided as well. The denominator of the reason will be the number of subjects not complete the study.

The number of subjects in Full Analysis Set, and number of subjects in PP population will also be presented with count and percentage. The denominator of the percentage will be the number of eligible subjects.

### 9.2 Protocol Violations and Deviations

This is a PMS study. Investigator could follow their practice and judgment. No protocol violation and deviation will be defined.

### 9.3 Demographic and Baseline Characteristics

The demographic characteristics including reimbursement status, date of birth, gender, race, education level, height, weight, concomitant diseases/comorbidities, risk factors, and medical history related to NVAF, Concomitant Therapies Related to CHA2DS2-VASc and HAS-BLED, Lab Data Related to CHA2DS2-VASc and HAS-BLED, Duration of previous VKA treatment (Cohort A only), PACT-Q1 Questionnaire (Cohort B only), and PACT-Q2 Questionnaire (Cohort A only) will be collected at visit 1 (baseline). Age will be calculated based on the date of birth and date of informed consent.

$$\text{Age} = \frac{(\text{Date of informed consent} - \text{Date of birth})}{365.25}$$

BMI will be calculated based on the height and weight.

$$\text{BMI} = \frac{\text{Weight (kg)}}{\text{Height (m)}^2}$$

Gender, race, education level, concomitant diseases/comorbidities, risk factors, and medical history related to NVAF, Concomitant Therapies Related to CHA2DS2-VASc and HAS-BLED, Lab Data Related to CHA2DS2-VASc and HAS-BLED, Duration of previous VKA treatment (Cohort A only), PACT-Q1 Questionnaire (Cohort B only), and PACT-Q2 Questionnaire (Cohort A only) will be summarized as count and percentage. Demographics and baseline characteristic will be analyzed based on FAS.

## 9.4 Medical History

Medical history will be collected as Concomitant Diseases/Comorbidities at visit 1 (baseline). No coding or analysis item for medical history of subjects will be planned. The data listing will present the raw medical history record of subjects.

## 10 DEFINITION AND DETERMINATION OF ANALYSIS

### VARIABLES

#### 10.1 Treatment Exposure and Compliance

Treatment duration will be counted from the date of visit 1 to the discontinued date in the Pradaxa® / VKA Discontinuation page. For those continuing using study drug, Treatment duration will be counted from the date of visit 1 to the date of visit 3. Treatment duration will be summarized as continuous variables. The reason for treatment discontinuation will be summarized as categorical data.

#### 10.2 Primary Endpoint(s)

##### Cohort A (patients switched from VKA to Pradaxa®)

- Mean change in the PACT-Q2 scores at the second assessment (30-45 days) and the last assessment (150-210 days) compared to baseline assessment. The changes will be calculated as (PACT-Q2 scores at Visit 2 minus PACT-Q2 scores at visit 1, PACT-Q2 scores at Last Visit minus PACT-Q2 scores at visit 1).

##### Cohort B (patients newly initiated Pradaxa® or VKA)

- Mean difference in the PACT-Q2 scores at the second (30-45 days) and the last assessment (150-210 days) compared between 2 treatment groups. The difference will be calculated as (PACT-Q2 scores of *Pradaxa®* minus PACT-Q2 scores of VKA at Visit 2, PACT-Q2 scores of *Pradaxa®* minus PACT-Q2 scores of VKA at Last Visit).

#### 10.3 Secondary Endpoints

##### Cohort A (patients switched from VKA to Pradaxa®)

- Mean change in the PACT-Q2 score at the last assessment (150-210 days) compared to the second assessment (30-45 days). The change will be calculated as (PACT-Q2 scores at Last Visit minus PACT-Q2 scores at visit 2).

##### Cohort B (patients newly initiated Pradaxa® or VKA)

- Description of mean PACT-Q1 score at baseline.

## 10.4 Safety Endpoints

- AEs (i.e. Pradaxa® relevant ADR (serious and non-serious), fatal AEs, and pregnancies)

Safety analyses will be performed separately for Cohort A and Cohort B.

The following parameters will be included in the safety analyses:

- Adverse drug reactions
- Adverse drug reactions leading to discontinuation of anticoagulation treatment
- Serious adverse drug reactions
- Adverse events leading to deaths

DRAFT

## 11 STATISTICAL METHODS

### 11.1 Primary Hypothesis

This study is aim to describe the treatment perception from patients with non-valvular atrial fibrillation (NVAF) receiving Pradaxa® or VKA for stroke prevention by using the self-estimation questionnaire of PACT-Q during a 6-month study period. The hypothesis for the testing is

$$H_0: \text{Change} = 0 \text{ vs. } H_a: \text{Change} \neq 0$$

### 11.2 Test of Assumptions

The primary hypothesis will be tested by paired t-test. The assumption of normality will be tested by using the Shapiro-Wilk test. Wilcoxon signed rank test will be used if the assumption of normally distributed is violated.

### 11.3 Primary Endpoint Analysis

Mean values and mean change from baseline of PACT-Q2 scores will be presented as descriptive statistics including Number, Mean $\pm$ SD, Median, Range, inter-quartile range (IQR), 25th percentile, 75th percentile and 95% C.I. The changes under Cohort A will be calculated as (PACT-Q2 scores at Visit 2 minus PACT-Q2 scores at visit 1, PACT-Q2 scores at Last Visit minus PACT-Q2 scores at visit 1). The difference under cohort B will be calculated as (PACT-Q2 scores of Pradaxa® minus PACT-Q2 scores of VKA at Visit 2, PACT-Q2 scores of Pradaxa® minus PACT-Q2 scores of VKA at Last Visit). Shapiro-Wilk test will be conducted for testing the normality. If the null hypothesis of normally distributed of Shapiro-Wilk test is not reject, two-sided paired t-test will be performed and obtain the p-value. Significant level of the test will be set as 0.05. Once significant result of Shapiro-Wilk test is lower than 0.05, Wilcoxon signed rank test will be used instead.

For cohort B, the patients newly initiated Pradaxa® or VKA will be matched with a ratio of 1:1 based on the propensity score with caliper matching. After the propensity score each patient is generated, both Pradaxa® group and VKA group should be randomly sorted and then the first VKA unit is selected to find its closest

Pradaxa® match in terms of the propensity score. The random seed will be set as 20190218. The caliper will be set as 0.001.

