9.3.3 Covariates

Demographic and clinical characteristics, including age, gender, body weight, CHA2DS2-VASc score, HAS-BLED score, kidney function (creatinine clearance), stroke and/or bleeding related risk factors, co-morbidities, and/or concomitant therapies will be collected if available. If any covariates or confounding/interacting variables that may be possibly predictive of the outcome under study are noted, additional analyses may be carried out to identify its effect. Details of handling covariates will be given in the statistical analysis plan (SAP), if any covariates of interest are detected.

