9.7.1 Main analysis

Baseline demographic and clinical characteristics

Descriptive summary will be presented for baseline demographic and clinical characteristics of all patients enrolled in Cohort A, Cohort B Pradaxa® initiators, and Cohort B VKA initiators, respectively. For continuous variables, number of patients, mean, standard deviation (SD), median, Q1 (lower quartile), Q3 (upper quartile), minimum, and maximum will be presented. For categorical variables, frequency and percentage will be presented for each category.

Primary outcomes

For Cohort A, descriptive summary will be presented for PACT-Q2 score at baseline visit (Visit 1), Visit 2, and Visit 3 using measure of central tendency and variation (mean \pm SD, or median with inter-quartile range (IQR)). The PACT-Q2 score at Visit 2 and Visit 3 will be compared with the PACT-Q2 score at baseline visit, respectively, using paired t-test or Wilcoxon signed-rank test based on the distribution of the data.

For Cohort B, the patients newly initiated Pradaxa® or VKA will be matched with a ratio of 1:1 based on the propensity score. The covariates age, gender, body weight, CHA₂DS₂-VASC score, HAS-BLED score, kidney function (creatinine clearance), stroke and/or bleeding related risk factors, co-morbidities, and/or concomitant therapies, **if available**, will be included in the propensity score model. Details of the propensity score model and the matching procedure, such as the choice of algorithm and caliper width will be specified in the SAP. Descriptive summary of the baseline characteristics will be presented for and compared between the matched patients to check the balance of baseline characteristics between the two groups of Cohort B after propensity score matching. Moreover, standardized difference will be calculated as a measure of the balance of baseline characteristics after propensity score matching. Analyses of PACT-Q2 score will be performed on propensity score matched Pradaxa® initiators and VKA initiators. Descriptive summary will be presented for PACT-Q2 score at Visit 2 and Visit 3 using mean \pm SD, or median with IQR. PACT-Q2 score will be compared between matched Pradaxa® initiators and VKA initiators using paired t-test or Wilcoxon signed-rank test.

Secondary outcomes

For Cohort A, the PACT-Q2 score at Visit 2 and Visit 3 will be compared using paired t-test or Wilcoxon signed-rank test based on the distribution of the data.

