9.9 LIMITATIONS OF THE RESEARCH METHODS

A non-interventional study is the most suitable design for obtaining information about the use of medicines in everyday therapeutic practice and thus for clarifying questions in everyday therapeutic practice. However, observational methodology inherits the limitation of selection bias and generalizability. In addition, the observational design intends to collect available data that are recorded on medical charts. The lack of data of interest may be one of the limitations.

A number of different types of bias that could influence the data collection and analysis from these cohorts are summarized below. Consecutive enrolment will be employed to minimize selection bias. The entry criteria are non-restrictive and will permit the enrolment of a broad patient population. The choice of treatment is at the discretion of the investigator. Missing data will be handled as appropriate (see Section 9.7.4) to lower the effect of missing values. All efforts will be made to minimize loss to follow-up in patients who are enrolled. Adjustment for covariates and propensity score matching (PSM) will be used to correct for identified confounders and channeling bias which could occur due to preferential prescribing in relation to different risks for events of interest (e.g. if Pradaxa® is prescribed more frequently to high risk patients than to other treatments, a high rate of outcome events could be expected in the Pradaxa® group). Patient reported outcomes will be assessed using validated questionnaires within a limited period of time to minimize recall bias which refers to the phenomenon when the outcomes of treatment (either good or bad) may colour the patient's recollection of events prior to or during the treatment.

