## 8.4 Covariates and Subgroups

Demographic and clinical characteristics, including age, gender, BMI classification (BMI<18.5, 18.5≤BMI<24, 24≤BMI<27, BMI≥27), CHA2DS2-VASc score, HAS-BLED score, kidney function (creatinine clearance), stroke and/or bleeding related risk factors, will be

considered as covariates/predictors for conducting propensity score matching the two subgroups in cohort B.

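### Protocol 9.9 names covariate adjustment alongside propensity matching, but protocol 9.7.1 and SAP 11.3 give only an unadjusted paired test for Cohort B, and nothing follows from the balance check

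*SAP*

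**What the plan says.** - Protocol 9.9 names two tools: "Adjustment for covariates and propensity score matching (PSM) will be used to correct for identified confounders and channeling bias".
- Protocol 9.3.3 allows additional covariate analyses and passes them on conditionally: "Details of handling covariates will be given in the statistical analysis plan (SAP), if any covariates of interest are detected".
- Protocol 9.7.1 specifies the Cohort B test without adjustment: "PACT-Q2 score will be compared between matched Pradaxa® initiators and VKA initiators using paired t-test or Wilcoxon signed-rank test". The abstract says the same.
- Protocol 9.7.1 also asks for a balance measure: "standardized difference will be calculated as a measure of the balance of baseline characteristics after propensity score matching". It gives no threshold and no next step.
- SAP 8.4 gives covariates one use; they are "considered as covariates/predictors for conducting propensity score matching the two subgroups in cohort B".
- SAP 11.3 tests the matched difference: unless Shapiro-Wilk rejects normality, a "two-sided paired t-test will be performed and obtain the p-value".
- SAP 8.7, under the heading on multiplicity, contains the only balance step in the SAP: "The baseline characteristics will be compared between the matched patients to check the balance of baseline characteristics". It names no metric, and SAP 11.3 does not refer to the result.
- SAP 12 declares no differences from the protocol.

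**The concern.** Cohort B is a non-randomised comparison, and protocol 9.9 is where the sponsor explains how channeling will be handled. One of the two safeguards named there has no implementation in any analysis section. The other is checked, but the same unadjusted pair difference is reported whatever the check shows.

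At most 200 pairs can be formed. An imbalance in age, CHA2DS2-VASc, HAS-BLED or creatinine clearance in the matched sample therefore carries into the reported difference in that dataset, and outcome variance that covariates could explain stays in the standard error. If the score is misspecified or leaves out a confounder, matching on it offers no second line of defence. Without a rule set in advance, any adjustment would be chosen after the imbalance, and perhaps the result, had been seen.

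**Working it through.** **Inputs from the documents.** 500 Pradaxa and 200 VKA initiators expected (SAP 7.4), so at most 200 pairs; 1:1 matching in random order, caliper 0.001 (SAP 11.3); two-sided 0.05 (protocol 9.7). The documents state no power, SD or effect size, so there is no planned figure to reproduce.

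**Assumptions.** Outcome SD 1; covariates explain R2 = 0.1 to 0.3 of PACT-Q2 variance; 8 independent covariates; caliper on the probability scale; 0.1 as the usual flag for a standardized difference (not in the documents).

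**1. Chance imbalance.** The SD of one standardized difference under pure chance is sqrt(2/n).
- n = 200: 0.100; P(above 0.1) = 32% per covariate; at least one of 8: 1 - 0.683^8 = 95%.
- n = 152: 0.115; 38%; 1 - 0.617^8 = 98%.
- n = 129: 0.125; 42%; 1 - 0.578^8 = 99%.
- n = 110: 0.135; 46%; 1 - 0.542^8 = 99%.

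**2. Idealised precision gain.** Adjusted SE = unadjusted SE x sqrt(1 - R2). With 200 pairs and no within-pair correlation, the difference detectable with 80% power is (1.960 + 0.842) x sqrt(2(1 - R2)/200).

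| R2 | SE factor | Detectable difference (SD) | Power at 0.25 SD |
|---|---|---|---|
| 0 (unadjusted) | 1 | 0.280 | 70.5% |
| 0.1 | 0.949 | 0.266 | 75.0% |
| 0.2 | 0.894 | 0.251 | 79.8% |
| 0.3 | 0.837 | 0.234 | 84.8% |

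**3. Simulated SAP procedure.** 700 patients, 8 covariates all in a correctly specified logistic score, random-order nearest match, caliper 0.001, no missing outcomes, R2 0.1 to 0.3.

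| Adjusted analysis | Runs per setting | Pairs kept | At least one covariate above 0.1 | Reported SE | Sampling SD |
|---|---|---|---|---|---|
| OLS in matched sample | 300 | 129-152 | 74-86% | unadjusted 4-17% larger | not recorded |
| Pair difference on covariate differences, moderate channeling | 400 | about 148 | 73-76% | falls 3-13% | changes from +1% to -5% |
| Same, strong channeling | 400 | about 110 | 92-95% | falls 2-12% | falls 0-8% |
| Linear model, pair-clustered SE | 600 | about 125-147 | 77-87% | falls 4-15% | falls about 2-9% |

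The largest SE contrast is 0.123 against 0.105: 0.123/0.105 = 1.17, so the unadjusted SE is 17% larger, which is the same as a 15% reduction. When outcome and treatment choice depend on the covariates in the same direction, a pair-clustered SE gained only about 0-3%. In that case pairs matched on the score are already alike on what drives the outcome, and the paired test uses this.

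Sampling SD is the better guide. In the 400-run setting with R2 0.3 and moderate channeling, the adjusted SE (0.099) fell below the sampling SD (0.110), and the adjusted test rejected in 8.2% of runs with no true effect.

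Mean bias was near zero in every 400-run setting (at most 0.015 SD in absolute value). In the 600-run variant, adjustment moved the individual estimate by 0.02-0.04 SD on average, and by 0.05-0.08 SD or more in one study in ten, against an SE of about 0.12.

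**4. Covariates outside the SAP score.** The score in protocol 9.7.1 may include body weight, co-morbidities and concomitant therapies, if available. SAP 8.4 replaces weight with four BMI classes and lists neither co-morbidities nor concomitant therapies as such, although some co-morbidities enter through the risk scores and risk factors. The simulations put every confounder in the score, so they do not cover this case.

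**The case against.** The strongest answer is that SAP 11.3 does what the protocol's analysis section says. Protocol 9.7.1 and the abstract specify the same paired test, and protocol 9.3.3 makes further covariate analyses conditional. A reader might infer that the SAP departs from the protocol on the primary test and that SAP 12 conceals it. The documents do not support that: on the test itself the SAP follows 9.7.1, and the conflict lies inside the protocol, between 9.9 and 9.7.1. The conflict remains, because 9.9 joins the two methods with an and; reading matching as the adjustment makes one of them redundant.

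A reader might also take the 74-86% of simulated studies with a covariate above 0.1 as proof that matching fails. It is not. Pure chance with 8 covariates would give 95-99% at 129-200 pairs, so matching balances better than randomisation would at that size. Nor is systematic bias shown: with every confounder in the score it averaged near zero, and the paired SE already reflects chance imbalance.

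Three further points stand. Nothing in the documents says how strongly these covariates predict PACT-Q2, so the precision figures are assumptions. The 0.001 caliper costs more: the SE rises from 0.100 with 200 pairs to about 0.115 or 0.135. And a paired test on matched pairs is a recognised analysis in a study that calls itself essentially descriptive.

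**Conclusion.** The point holds as an inconsistency and a gap in pre-specification. Protocol 9.9 names adjustment; protocol 9.7.1, the abstract and SAP 11.3 do not provide it; and the balance check has no consequence. The documents do not support a claim that the Cohort B estimate is biased, or that a fixed share of precision is lost.

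Under R2 of 0.1-0.3, the unadjusted reported SE is about 0-17% larger than the adjusted one, and the true sampling SD falls by about 0-9%. The top of each range is an upper figure, and both depend on how far the predictors of outcome and of treatment choice overlap. The stronger reason to adjust is protection where the simulations are favourable to the plan: a misspecified score, or a confounder that SAP 8.4 leaves out. The size of that benefit cannot be computed from the documents. The change should be made, but it does not invalidate the planned comparison.

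**What to change.** - **SAP 11.3, Cohort B.** At Visit 2 and Visit 3, pre-specify a linear model in the matched sample with treatment plus the covariates of protocol 9.7.1 and SAP 8.4, and SE clustered on pair. Report it together with the protocol's paired t-test or Wilcoxon result. State that the Shapiro-Wilk switch applies only to the paired test, how overlapping covariates are coded (CHA2DS2-VASc already contains age and sex), and how missing covariates are handled.
- **SAP 8.7.** Report standardized differences, as protocol 9.7.1 requires. Set a threshold, for example 0.1, and state in advance that the adjusted estimate is the one interpreted if any covariate exceeds it. At 0.1 the simulations suggest that this will usually happen, so the threshold should be chosen with that in mind.
- **Alignment.** Bring protocol 9.7.1 (with the abstract) and 9.9 into agreement, and record the added analysis in SAP 12.

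The cost is one model per visit on covariates already planned for collection where available, plus wording in both documents. The downsides are a model-based estimate beside the raw pair difference, and a declared change from protocol 9.7.1. It should be settled before the matched outcomes are examined.
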